4.6 Strategies for Recruitment and Retention

Participants will be recruited from the outpatient clinic of the Weill Cornell Institute of Geriatric Psychiatry, community-based mental health services, community-based medical practices, and other community organizations.

Additionally, participants may be recruited through the Epic MyChart subject pool, protocol #18120119822 ("Collecting Patient Consent to be Contacted for Research"). Patients in this subject pool have given consent to be contacted about research studies based on the information in their electronic medical record.

We will also recruit participants through social media ads on Facebook and Instagram. We have used a similar approach in two active protocols #1802019007 and #1708018441. Participants who press on our social media ad will be presented with a brief Qualtrics survey, managed in collaboration with JCTO specialist, [name], where participants can fill in their information and contact details if they choose to be contacted by a research assistant to discuss voluntary participation. Participants will also receive a link to the JCTO page of the study, as previously noted. Qualtrics is used via Weill Cornell's approved resources. The PI will monitor responses to the survey.

Eligible individuals will be invited to participate in the study after providing informed consent. Individuals who do not meet criteria may be offered participation for other research studies or given referrals for treatment in the community if desired.

Recruitment of WCM clinicians:

We will recruit four Masters-level therapists from those working on other psychotherapy projects at the Weill Cornell ALACRITY Center. Therapists will be certified to provide "Engage & Connect" or SRP and will be unaware of study hypotheses. Training will follow the Institute's training procedures and fidelity standards. Our previous work has shown that therapists with this level of training and clinical experience can be trained in "Engage" and maintain high fidelity.³⁰ Training procedures are described below. Therapists and research assistants administering clinical rating will remain unaware of study hypotheses. Therapists will be responsible for completing the Patient Health Questionnaire (PHQ-9) at the beginning of each session to monitor patients' clinical states. At the end of each session, they will complete the "Working Alliance Inventory-12" (WAI-12) to evaluate the quality of the working relationship at each session. Additionally, they will complete the MULTI at Baseline, Week 3, 5 and 9 to evaluate their use of therapeutic techniques.

All therapists are service providers on this protocol and are employed by Weill Cornell Medicine's Geriatric Psychiatry Institute or participate in activities at the Geriatric Institute either full-time, part-time, or on a contract basis. Thus, they are all paid for their time regardless of whether they participate in this research study or not. Therapist service providers are given the option to participate in this or any other research study that aligns with their interests, skills, schedule, and the clinical training it provides. If they are not interested, they are welcome to continue working on other services and research projects at the Institute. Therapists' involvement is voluntary and in addition to their primary duties at the Weill Cornell ALACRITY Center. We are seeking informed consent from the therapists to collect basic data related to their training background (e.g., training history, years of experience, theoretical orientation), completion of research assessments, and use of study interventions. Their participation will be voluntary, and their information will be kept confidential. Information regarding the therapists' performance in the study will not be shared with employers outside of the study. Of particular importance is the need to ensure that the therapist understand that their decision to participate (or to withdraw participation as therapists on the study) will have no job ramifications.

WCM clinicians working on other similar psychotherapy trials will be offered the opportunity to

participate in the study as therapists. They can choose not to participate without any negative consequences to their employment or benefits. Clinicians' direct supervisor will not be involved in the study activities and thus the main supervisory relationship will not be affected by study participation. Participating therapists are not the subjects of the research intervention per se, and we will not collect medical or psychiatric information about them. We consent the providers because they are administering clinical scales to monitor patients' progress during the study period when they are delivering the study interventions (e.g. depression symptoms, suicide risk).

Patients participating in this study will be compensated approximately \$345 for completion of the study. This amount is equivalent to similar ongoing studies in our department:

- \$30 for each research assessment (\$120 total)
- \$75 for each MRI assessment (\$225 total)
-

Participants could be reimbursed for travel to and from study visits if needed.

5. Registration Procedures

5.1 Subject Registration (WCM only)

Subjects will be registered within the WRG-CT as per the standard operating procedure for Subject Registration. Data will be tracked on RedCap. Clinical notes by clinicians will be tracked in Epic.

5.2 Subject Registration (Sub-sites)

For multicenter studies with a WCM as the coordinating site, please contact [contact] for template language for participate site registrations

6. Study Procedures

6.1 Schedule of Assessments

Patient participants will be randomized to receive a 9-week course of either weekly Engage & Connect therapy or SRP, and research assessments will be conducted at baseline and weeks 3, 5, and 9.

| Week | Baseline | 1 | 2 | 3 | 4 | 5 | 6 | 7 | 8 | 9 |
|----------------------------|----------|---|---|---|---|---|---|---|---|---|
| Therapy Session | | x | x | x | x | x | x | x | x | x |
| Research Assessment | x | | | x | | x | | | | x |
| MRI Scans | x | | | | | x | | | | x |

Trained research assistants unaware of study hypotheses will collect weekly clinical and self-report ratings at each study time point.

| Instrument | Baseline | Week 1 | Week 3 | Week 5 | Week 9 |
|---|----------|--------|--------|--------|--------|
| Demographics | | | | | |
| Demographic questionnaire | x | | x | x | x |
| Brief Antidepressant Questionnaire (BAQ) | x | | x | x | x |
| Intent to Complete | x | | | | |
| Depression Severity and Anhedonia | | | | | |
| Montgomery Åsberg Depression Rating Scale (MADRS) | x | | x | x | x |
| Hamilton Depression Severity Scale (HAMD) | x | | x | x | x |
| The Dimensional Anhedonia Rating Scale (DARS) | x | | x | x | x |
| Behavioral Activation and Reward Measures | | | | | |
| Behavioral Activation for Depression (BADS) | x | | x | x | x |
| Anticipatory and Consummatory Interpersonal Pleasure Scale (ACIP) | x | | x | x | x |
| Clinical Characteristics | x | | | | |
| Mini-Mental State Examination (MMSE) | x | | | | |
| Interpersonal Problems Inventory – 32 items (IIP-32) | x | | | | x |
| Duke Social Support Index | x | | x | x | x |
| Revised UCLA Loneliness scale | x | | | | x |
| Treatment Rationale Scale | | x | | | |
| MRI tasks | x | | | x | x |
| Probabilistic Reversal Learning task | x | | | x | x |
| Social Incentive Delay task | x | | | x | x |
| Adverse Event Evaluation | | x----- | | | x |

Trained research assistants unaware of study hypotheses will collect weekly clinical and self-report ratings at each study time point via zoom, and in person assessments will be offered if needed.

- **Demographics:** Our demographics questionnaire includes age, gender, race, religion, living conditions, marital status, occupation, birth place, and education.
- **Medication List and History of Antidepressant Treatment:** The medication list will also help the RA assess medical comorbidity. The Brief Antidepressant Questionnaire (BAQ) is used to evaluate frequency, dosage, and duration of antidepressant treatment for the past 3 months.
- **Intent to Participate:** At baseline, the participants will be asked about their intent to complete the study.
- **Mini-Mental State Examination (MMSE):** This brief cognitive screen will be used to screen for the presence of cognitive impairment. Participants will need to receive a score equal or above 1 SD below the mean score for patient's age and education, or DSM-5 criteria.
- **Working Alliance:** The Working Alliance Inventory (WAI) is an assessment of the

working relationship (“alliance”) between the patient and the therapist ³¹. The WAI is administered to the patient at baseline and to both the patient and the therapist after each session.

- **The Multitheoretical List of Interventions:** The MULTI is an assessment of use of therapeutic techniques delivered by the therapist.³² The MULTI will be filled out by the therapist at Baseline, Week 3, Week 5, and Week 9.
- **Anhedonia:** The Dimensional Anhedonia Rating Scale (DARS) is a self-report scale assessing hedonic response over the previous few days.³³
- **Behavioral Activation:** The Behavioral Activation for Depression Scale (BADS) is designed to measure behaviors related to rewarding experiences that are targeted in therapies like Engage.³⁴
- **Depression Severity:** The Montgomery-Asberg Depression Rating Scale ³⁵, a 10-item severity scale, will be used to measure symptom severity. The MADRS is sensitive to change and is appropriate for depressed elders. It also allows us to assess suicidal ideation and level of risk. We will also use the Hamilton Depression Severity Scale, a 17-item measure that is widely used and well validated.³⁶
- **The Dimensional Anhedonia Rating Scale (DARS):** The DARS is a 17-item measure which will be used to measure severity of anhedonia and changes in severity over time.³³
- **Interpersonal Problems:** The Interpersonal Problems Inventory – 32 items (IIP-32) assesses difficulties in interacting with other people ³⁷.
- **Social Support:** The Duke Social Support Index will be used to assessed patients' subjective and instrumental support and amount of social interaction.³⁸
- **Loneliness:** The Revised UCLA Loneliness Scale will be used to measure patients' perceived sense of loneliness.³⁹
- **Anticipatory and Consummatory Interpersonal Pleasure Scale (ACIP):** A 17-item questionnaire aimed to evaluate patients' anticipatory and consummatory pleasure associated with social and interpersonal interactions with others
- **Treatment Rationale Scale:** A 4-item measure will be used to evaluate patients' expectations of the potential benefits of treatment.^{40,41}

MRI Tasks

- **Probabilistic Reversal Learning (PRL) Task:** This task is aimed to measure prediction error and affective salience. In this task, participants select between two simultaneously presented stimuli and receive positive or negative feedback following their response selection. They must learn, through trial and error, which stimulus dimension (color or category) is more likely to lead to positive feedback.^{42,43} This task is widely used in the literature and is a component of NIMH's RDoC matrix learning criterion.
- **Social Incentive Delay Task (SID):** We developed a novel SID task, modeled after the Monetary Incentive Delay task (MID), which we will use for our exploratory analyses.^{44,45} The SID examines social reward anticipation and receipt (Figure 7). On incentive trials, the participant sees a cue stimulus, human face silhouette, indicating an anticipated social reward. Then, he/she responds as quickly as possible with a button press during target stimulus presentation (White Square). Fast response time is rewarded with ‘thumbs up’ and happy face. Slow response is punished ‘thumbs down’ and sad face. On neutral trials, all performance is followed by a neutral face. The SID includes two social reward conditions: a) Standard: feedback from a stranger; b) Personalized: feedback from the patient's therapist (i.e. an individual with likelihood of a high social reward

value).

6.1.1 Screening Visit + Baseline (*several days before start of treatment*)

Screening will include the Major Depression Module and the Screener from the SCID-V to ensure the participant meets the clinical criteria (see exclusion and inclusion criteria section)

- Informed consent
- Medical history and medication history
- Demographic questionnaire
- Brief Antidepressant Questionnaire (BAQ)
- Intent to Complete
- Depression Severity and Anhedonia
- Montgomery Åsberg Depression Rating Scale (MADRS)
- The Dimensional Anhedonia Rating Scale (DARS)
- Behavioral Activation for Depression (BADS)
- Anticipatory and Consummatory Interpersonal Pleasure Scale (ACIP)
- Mini-Mental State Examination (MMSE)
- Interpersonal Problems Inventory – 32 items (IIP-32)
- Duke Social Support Index
- Revised UCLA Loneliness scale

MRI tasks

- Probabilistic Reversal Learning task
- Social Incentive Delay task

6.1.2 Treatment Phase

Monitoring of Clinical State

Study participants' clinical state will be monitored by their study therapists. Therapists and their supervisor will discuss symptoms that may require treatment other than that provided by the study. The supervisor will also be available for phone calls with therapists between supervision sessions. If a participant requires additional care, the therapist and supervisor will collaborate on a referral.

Therapists will administer the Patient Health Questionnaire (PHQ-9) during each therapy session. If a participant endorses suicidal ideation or behavior on item 9 of the PHQ-9 ("Thoughts that you would be better off dead, or of hurting yourself"), the therapist will conduct a thorough safety evaluation. If the therapist determines that the participant is at risk, the therapist will consult with a supervisor and/or with the director of the Weill Cornell Institute of Geriatric Psychiatry to determine a course of action.

Additionally, research assistants will administer the MADRS during research assessments. If a participant endorses suicidal ideation or behavior on item 10 of the MADRS ("This past week, have you felt like life isn't worth living?"), the research assistant will complete the Suicide Risk Assessment protocol (see attachments), which has been approved by NIMH for determining an increase in suicidal ideation. The research assistant will then report the results of the Suicide Risk Assessment to the

participant's study therapist or another clinician in the Institute of Geriatric Psychiatry, who will conduct a thorough safety evaluation if warranted.

Depending on the level of risk, the participant may be encouraged to speak to his/her own clinician; the PI or therapist may call the participant's clinician and/or family member; or the participant may be referred for an evaluation by a clinician who will conduct a thorough assessment via phone or video. . Other urgent risks may necessitate calling 911 or having a family member bring the participant to a local emergency room for evaluation.

6.1.2.1 Visit 1 (baseline; Cycle 1 Day 1)

Assessments will be administered based on assessment schedule above over the course of 9 weeks (See SoA above).

6.1.2.2 Visit 2 (\pm X day(s))

Assessments will be administered based on assessment schedule above over the course of 9 weeks (See SoA above).

6.1.3 Follow-up Phase

Not Applicable

7. Study Intervention

7.1 Study Intervention/Device Description

We will randomize participants to 9-weeks of either weekly "Engage & Connect" therapy or Symptom Review and Psychoeducation (SRP) provided by licensed or license-eligible clinicians (at least Masters-level social workers or mental health counselors). Therapists will receive training and weekly supervision from the PI in collaboration with a licensed clinical psychologist and member of our research team, to ensure adherence to treatment protocols and address clinical issues. Trained research assistants, unaware of study hypotheses, will assist in administration of ratings and scanning procedures.. Interventions will be delivered via video or phone, in accordance with the institutional policy.

Participants may be lent a tablet during their participation in the study to facilitate remote sessions if they do not have adequate technology at home. When possible, participants may be asked to use a wearable device that we provide during their participation in the study. The wearable device allows for passive sensing of movement (steps), heart rate, and sleep daily. Participants and therapists may be able to review their activity for the week to augment the sessions. Data will be collected from the device's corresponding mobile app (e.g., device-linked app commercially used to extract steps, sleep, and heart rate as described above). No investigational devices or apps will be used to collect or extract data, and the device will be used in accordance with its approved and marketed use.

At the end of the study, participants are required to return the mobile and/or wearable devices. This technology and platform are being used successfully in the other IRB-approved studies at our

ALACRITY center (19-09020810; 19-09020854).

“Engage & Connect”

“Engage” targets the PVS system using ‘reward exposure’ intervention – engagement in rewarding activities implemented in weekly ‘action plans’ developed by the depressed patient and the therapist.²² In patients with negativity bias, apathy, or inadequate emotional regulation, therapists provide targeted interventions so that reward exposure proceeds unimpeded. “Engage & Connect”, a modified adapted version of “Engage”, focuses on exposure to rewarding activities with significant others. During sessions, the therapist and patient will select a social activity (i.e. interaction with a significant other) and formulate a stepped plan to complete this goal. By week 3, therapists will assess patients’ barriers to reward exposure – negativity bias, apathy, inadequate emotion regulation, as well as interpersonal conflicts and social skills deficits, which may hinder social interactions – and address barriers through targeted strategies.

Symptom Review and Psychoeducation (SRP)

SRP is a comparison condition that resembles what a good clinician does in evaluating, reassuring, and educating a depressed patient. Each session begins with reviewing the depressed patient’s symptoms, then assessing patient’s knowledge base about depression. Identifying patient’s misconceptions about depression will guide the selection of educational material to be presented in each session. Comprehending depression-related information is contaminated by pessimism, denial, misconceptions, and stigma. The role of SRP therapist is to impart valuable information, despite these complexities. Conveying information is a process. The SRP therapist needs to be aware of “where the patient” is and offer information for which he/she has readiness to accept. SRP therapists do not engage in other interventions. Arguably, SRP is a condition with: 1) non-specific active therapeutic ingredients; 2) little overlap with the therapeutic ingredients of “Engage & Connect”; and 3) exposure of patients to therapists equal to that of “Engage & Connect”. We used a similar comparison condition in a recently completed psychotherapy study of post-stroke depression and found that SRP leads to reduction in depression severity (R01 MH096685, PI: [name]).

7.2 Availability

Not Applicable

7.3 Acquisition and Accountability

Not Applicable

7.4 Formulation, Appearance, Packaging, and Labeling

Not Applicable

7.5 Product Storage and Stability

Not Applicable

7.6 Preparation

Not Applicable

7.7 Dosing and Administration

All participants will receive 9- weeks of psychotherapy, either “Engage & Connect” or “SRP”, as indicated above.

7.7.1 Dosing Delays/Dose Modifications

Not Applicable

7.8 General Concomitant Medication and Supportive Care Guidelines

Not Applicable

7.9 Duration of Therapy and Criteria for Removal from Study

In the absence of treatment delays due to adverse event(s), psychosocial interventions will continue for a period of 9 weeks.

7.10 Duration of Follow Up

Participants who choose to discontinue the study will be asked and encouraged to complete research assessments for the remaining weeks per their agreement.

7.11 Measures to Minimize Bias: Randomization and Blinding

Participants will be randomly assigned to 9-weeks of either “Engage & Connect” psychotherapy or “SRP” psychotherapy. Therapists and research assistants administering clinical rating will remain unaware of study hypotheses. Trained research assistants unaware of study hypotheses will collect weekly clinical and self-report ratings at each study time point.

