Procedures for management of suicide risk: We will exclude participants who endorse intent or plan to attempt suicide in the near future at screening. During the study, participants' clinical state will be monitored by their therapists. Therapists and their supervisor will discuss symptoms that may require treatment other than that provided by the study. Therapists will administer the Patient Health Questionnaire (PHQ-9) during each therapy session. If a participant endorses suicidal ideation or behavior on item 9, the therapist will conduct a thorough safety evaluation. If the participant is at risk, the therapist will consult with a supervisor to determine a course of action. Additionally, the research assistant (RA) will administer the MADRS during research assessments. If a participant endorses suicidal ideation or behavior on item 10, the RA will complete the Suicide Risk Assessment protocol, approved by NIMH for determining an increase in suicidal ideation. The research assistant will then report the results to the study therapist, the PI, and the supervisor, who will conduct a thorough safety evaluation if warranted. Depending on the risk, the PI or therapist may call the participant's clinician and/or family member; or the participant may be referred for an evaluation by a study clinician available at the time via phone or video. Other urgent risks may necessitate calling 911 or having a family member bring the participant to a local emergency room for evaluation.

Procedures for managing incidental clinically significant MRI findings: All MRI scans will be read by a board-certified Weill Cornell Medicine neuroradiologist. If a clinically significant finding is identified, an MD clinician investigator on the study protocol will notify the participant (in person or via phone call) and discuss the finding. With the participant's permission, his/her primary care physician will be notified by the PI, and the participant will be informed and advised to take clinically appropriate action. The proposed MRI scan sequences are not optimized for diagnostic purposes and might not reveal all clinically significant abnormalities. Participants are informed that the MRI scan is not intended for diagnostic purposes, thus, undergoing the MRI scanning session is not comparable to receiving a clinical MRI exam.

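### MADRS raters are masked to the study hypotheses but nowhere to treatment arm, so any between-arm MADRS comparison is open to rater bias

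*Combined protocol and SAP*

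**What the plan says.** Section 7.11 states the masking rule in one sentence: "Therapists and research assistants administering clinical rating will remain unaware of study hypotheses". Section 6.1 repeats it for data collection: "Trained research assistants unaware of study hypotheses will collect weekly clinical and self-report ratings at each study time point via zoom", with in-person visits offered where needed. Section 4.6 applies the rule to therapists, who are certified in Engage & Connect "or SRP and will be unaware of study hypotheses". Section 7.1 applies it to the research assistants who "will assist in administration of ratings and scanning procedures".

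On who scores the scale, section 6.1.2 says "research assistants will administer the MADRS during research assessments". A second depression rating is also collected: "We will also use the Hamilton Depression Severity Scale, a 17-item measure" (section 6.1).

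Change in MADRS over 9 weeks is a secondary endpoint (1.2.5) and is tested as H3 (12.1). Section 10 lists depression severity, resting-state connectivity (rsFC) and behavioral activation (BADS) as the measures of treatment effect. The synopsis and section 12.1 describe a randomized comparison of two interventions.

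**The concern.** Keeping a rater from the hypotheses is weaker than keeping the rater from the arm. A rater who knows or guesses the arm can form an expectation without being told what the investigators predict. Here the arms are easy to tell apart from a patient's description: one plans social activities with significant others, the other reviews symptoms and teaches about depression (7.1).

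If scoring leans with the arm, the lean is built into the recorded score. No model can separate it from a treatment effect. At stake is the clinical outcome of a trial presented as a comparison. SH is also exposed, because it uses MADRS as the dependent variable and predicts relationships in Engage & Connect that should be absent in SRP (12.1).

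**Working it through.** The plan gives no figure on this point, so the check is a reading of the text plus one count.

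**1. Could the wording in 7.11 mean masking to arm?** No. The same sentence covers therapists and raters. Therapists are trained in a named intervention and deliver it (4.6, 7.1, 7.12), so they know the arm. A rule that they satisfy does not conceal the arm from anyone else it covers.

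**2. Does another section add masking to arm?** Sections 4.6, 6.1 and 7.1 refer only to the hypotheses. Sections 6.1.2 and 13.1, which describe the MADRS interview and what follows from it, say nothing on masking. No section asks patients not to reveal their therapy or provides for recording unmasking. Front-matter pages and the schema figure were not available, but section 7.11 is complete.

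**3. Which measures depend on a rater?**
- rsFC (primary): measured by MRI.
- BADS (secondary): described as self-report (3.1). Research assistants collect it, and the documents do not say whether items are read aloud, but the answers are the patient's.
- MADRS (secondary): administered by research assistants. It is the only rater-scored measure of the three.

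**4. How might a rater learn the arm?**
- *Patient disclosure* is the main route that the plan leaves open. The schedule in 6.1 places the Duke Social Support Index, which covers amount of social interaction, and an interpersonal pleasure scale at the same Week 3, 5 and 9 assessments as the MADRS. The visit therefore raises the subject that distinguishes the arms.
- *Suicide-risk contact* is only a possible route. Section 13.1 says "The research assistant will then report the results to the study therapist, the PI, and the supervisor"; section 6.1.2 allows the report to go to the study therapist or to another Institute clinician. Information flows from rater to clinician. It reveals the arm only if the rater knows what that therapist delivers, and the documents do not say whether each therapist delivers one arm or both.
- *The Social Incentive Delay (SID) task* is also only a possible route. One condition gives feedback from the patient's own therapist (6.1), and research assistants help with scanning (7.1). Whether one assistant does both jobs for a patient is not stated.

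**5. Exposure.** Inputs: 60 patients, 30 per arm (1.1); post-baseline MADRS at Weeks 3, 5 and 9 (table in 6.1). Sections 6.1 and 7.11 call the ratings weekly, but the count follows the table.

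Scheduled post-baseline MADRS ratings = patients x visits = 60 x 3 = 180, or 30 x 3 = 90 per arm.

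This is neither a lower nor an upper bound. Attrition of about 10% (4.1) and missed visits reduce it. Continued assessment after discontinuation (7.10) limits that loss, and replacement of withdrawn patients (8.2) can add to the total. The HAMD is left out because it is not a listed endpoint.

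**6. Size of bias.** The documents give no MADRS standard deviation, effect size or rater-bias figure, so none can be computed.

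**The case against.** The strongest reply is that the harm needs a test the plan does not write down. H3 is worded as change during Engage & Connect, and the model for H1 to H3 lists a random intercept and time terms with no arm term (12.1, 12.4.1). This stands as a limit: the within-arm time effect in H3 is not the target of this point. It does not remove the point, because the trial is described as comparing two arms and SH contrasts them. For SH the limit is finer. A shift that is constant within an arm would not by itself alter a slope, but scoring that leans with time or with how activated the patient seems could.

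A second reply is that silence on arm is compatible with raters who are kept unaware in practice. That is true, and a reader might wrongly infer that the raters are unblinded or know the arm. The documents do not show this. They do state a masking rule, however, and it is the weaker one.

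Third, there are partial safeguards: masking to the hypotheses, and a comparator with equal therapist contact (7.1). They may weaken expectations, but neither conceals the arm. Rating by Zoom does not conceal it either, since patients can describe sessions on a call.

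Fourth, asking patients not to discuss their sessions could cut across the adverse-event inquiry required at each visit (13.4). This stands, and the remedy must leave that inquiry untouched.

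**Conclusion.** The point holds as a gap in the design. Raters of a secondary endpoint are masked only to the hypotheses, and nothing planned prevents or records their learning the arm. It bears on any between-arm MADRS comparison and on the SH contrast, with 180 scheduled post-baseline ratings exposed before attrition, missed visits or replacement.

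A reader might go further and infer that the trial's main result is compromised, or that a specific inflation of the false-positive rate follows. Neither is supported. The primary endpoint does not depend on a rater. An error rate would need an assumed rater shift with no basis in the documents, applied to a test the plan does not state.

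The conclusion rests on two assumptions: that a between-arm MADRS comparison will be made or read from the results, and that no unseen document masks raters to arm. The change should be made because it is cheap and cannot be made after the ratings are collected. In a pilot with an imaging primary endpoint, it is not a reason to doubt the trial as a whole.

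**What to change.** - In 7.11 and 6.1, state that research assistants scoring the MADRS and HAMD are masked to allocation and do not access arm information. The user and group privileges in REDCap (11.1.1) could enforce this.
- Before each rating, have the assistant ask the patient not to say which therapy they receive or describe session content. State that adverse-event inquiry and suicide-risk reporting are unchanged.
- Log any unmasking, with date and route, including through safety contacts.
- Where existing staffing allows, a patient's rater should not run that patient's therapist-face SID condition.

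The cost is protocol wording, one scripted line per rating and a short log. Raters and therapists are already separate roles. Use of research assistants becomes slightly less flexible. Their number is not given, nor whether raters also make reminder calls or keep the adverse-event log, so full separation may not always be possible. Some unmasking will remain, but it will be recorded.
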